Linear mixed effects modelling was used to establish whether there were differences in the outcomes of interest between the VR and control groups. Patient-level random effects were considered to account for the repeated outcomes measures. Interaction terms of participant exposure and time were included in each model and used to ascertain whether changes in the outcomes of interest from baseline - before each activity for the daily and before exposure to NPI for the weekly outcomes and at specific time points – during and after each activity for the daily and at day six for the weekly outcome measures – were different between the VR and non-VR groups. Baseline demographic characteristics and duration of exposure to each environment for the daily outcomes were considered for adjustment in the full models. Terms were sequentially removed from the full models if their exclusion did not affect model fit. Reduced models were compared to full models using the Akaike Information Criteria (AIC) and those with the lower values were identified as the final models for each outcome. Using the final models, adjusted values of each outcome per group were estimated and presented as mean summaries with standard errors as a measure of dispersion. The 95% confidence interval (CI) of the fixed effects were estimated using the bootstrapping method and graphical plots of residuals and fitted values were used to determine whether normality and constant variance assumptions were met. To explore potential correlations between video and audio fidelity, and cyber sickness between applications in the immersion survey a two-sample t-test was also used. All analyses were conducted using R statistical software. For more details on the statistical analysis plan, please refer to Appendix A.

Interim analyses

An interim analysis was completed in 2021 (n=52) and indicated no substantive difference between arms, and no significant adverse events. The study was continued to achieve the intended sample size.

Methods for additional analyses (e.g., subgroup analyses)

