The primary analysis will compare mean changes in daily pain before each immersion session and pain scores during and after each session in intervention group to mean changes in daily pain before each immersion session and pain scores during and after each session in control group. Difference in pain score before to time points where it is measured during and after each session (during and after) will be the dependent variable. Study participants will be considered as random effects, treatment group and time together with an interaction term of the treatment group and time as fixed effects. The estimated difference in mean change from before to during, and after immersion sessions and the corresponding 95 % confidence interval (CI) between groups will be presented.

Using a similar approach, the mean changes in weekly pain from baseline measured using the McGill Pain Questionnaire for the overall pain score – combining assessing sensory pain (11 items) and affective pain (4 items) as well as a VAS component scored out of 10, and separately for each component – in intervention group to mean changes in weekly pain in control group will be compared.

Secondary outcomes

Mean changes from baseline in weekly health related quality of life scores and sleep quality index measured using the Health Survey Short Form quality of life and Pittsburgh Sleep Quality Index respectively were compared between the intervention and control groups using the approach like that of weekly primary outcomes.

5. Missing data

When analyzing data for all study participants and those with severe pain, complete case analyses will be conducted for both primary and secondary outcomes. If the number of participants excluded due to missing demographic characteristics is >5% comparisons by assignment arm of those included and those excluded will be conducted to determine if there are any differences in drop out by arm.

References

1. Twombly, R. (2004). What's in a name: who is a cancer survivor? *Journal National Cancer Institute* 96: 1414-15.
2. Canadian Cancer Society and the National Cancer Institute of Canada. *Canadian Cancer Statistics 2008* Toronto: Canadian Cancer Society.

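### The daily-pain model may retain session duration, a post-randomisation variable, and the plan does not say whether it or Appendix A's model is primary

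*Combined protocol and SAP*

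**What the plan says.** The body text, under Statistical methods for primary and secondary outcomes, describes linear mixed models with group-by-time interactions. It states that "Baseline demographic characteristics and duration of exposure to each environment for the daily outcomes were considered for adjustment in the full models". Terms are then dropped one after another, full and reduced models are compared by AIC, and "those with the lower values were identified as the final models for each outcome". Results come from those models: "Using the final models, adjusted values of each outcome per group were estimated and presented as mean summaries with standard errors". The section closes its description with "For more details on the statistical analysis plan, please refer to Appendix A".

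Appendix A, section 4 (Primary outcome), says: "The primary analysis will compare mean changes in daily pain before each immersion session and pain scores during and after each session". The dependent variable is a change score ("Difference in pain score before to time points where it is measured during and after each session"). Participants are random effects, with "treatment group and time together with an interaction term of the treatment group and time as fixed effects". It mentions no duration term, covariate list or selection step. The only sign of covariates is in section 5 (Missing data), which has a rule beginning "If the number of participants excluded due to missing demographic characteristics is >5" per cent, and that concerns demographics only.

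On duration itself, Participant timeline says 30 minutes was a minimum that participants could exceed to finish a task. Plans for assessment and collection of outcomes says time spent was recorded daily with the pain scores. Intervention description says that for one of the four applications the control arm played a different puzzle game.

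**The concern.** Duration is not a baseline characteristic. It arises after allocation, is chosen by the participant, and can depend on platform and game. For the during-session score, which participants recall from around mid-session, total duration is settled only after the moment being rated.

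The objective in Appendix A, section 1, is how far VR is advantageous over 2D for daily home use. If VR keeps people engaged for longer or shorter, that is part of the comparison. Conditioning on duration removes it, and the estimate is then no longer the effect of assignment. AIC rewards fit and does not separate baseline covariates from consequences of treatment.

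Because the body text and Appendix A describe different models and neither is given precedence, a reader cannot tell whether the primary result is adjusted for duration. The intention-to-treat wording is not breached, since participants are still analysed as allocated. The issue is what the estimate means.

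**Working it through.** The plan gives no figure for duration by arm or for its relation to pain, so there is none to reproduce, and the inputs below are assumptions. From the plan come 50 participants per arm (Sample size), 24 session days (Appendix A, section 2) and the 10 mm MCID (Outcomes).

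**1. The two texts side by side**

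| | Statistical Methods | Appendix A, section 4 |
|---|---|---|
| Outcome | Values before, during and after; raw or change score not stated | Change from before |
| Core terms | Group-by-time; participant random effect | Group, time, group-by-time; participant random effect |
| Further candidates | Demographics, duration | None listed |
| Selection | Backward removal, lower AIC | None |
| Reported | Adjusted group values from the selected model | Difference in mean change with 95% CI |

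**2. Algebra**

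Let δ be the direct VR effect, Δ the VR-minus-2D difference in minutes, and s the fall in during and after pain per extra minute. The effect of assignment is δ − sΔ.

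- *Change-score model with duration:* it estimates δ, a shift of sΔ. This is 0 mm at Δ = 0; 5 × 0.1 to 5 × 0.3 = 0.5 to 1.5 mm at 5 minutes; 10 × 0.1 to 10 × 0.3 = 1 to 3 mm at 10 minutes.
- *Raw-score model with duration as a main effect:* duration takes the same value at all three time points, so the group-by-time contrast does not move. The fitted slope averages 0, s and s, which is 2s/3. The adjusted VR-minus-2D value after the session moves by 2sΔ/3: 10 × 0.1 × 2/3 = 0.7 mm, or 10 × 0.3 × 2/3 = 2.0 mm.
- *Raw-score model with a duration-by-time term:* the contrast moves as in the change-score model.

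**3. Simulation**

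Random-intercept models, 200 replicates per scenario, Monte Carlo SE about 0.1 mm. Assumed: δ = −5 mm; 2D mean 40 min; duration SD 5 min between and 6 min within participants; change SD 6 mm between participants, 8 mm at day level and 6 mm residual.

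Change score after the session (mm):

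| VR minus 2D (min) | s (mm/min) | Without duration | With duration |
|---|---|---|---|
| 0 | 0.2 | −4.9 | −4.9 |
| +5 | 0.2 | −5.9 | −4.9 |
| +10 | 0.1 | −6.0 | −4.9 |
| +10 | 0.2 | −7.0 | −5.0 |
| +10 | 0.3 | −8.1 | −5.1 |
| −5 | 0.2 | −4.1 | −5.1 |

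In the raw-score model at +10 min and 0.2 mm/min, the group-by-after contrast was −7.00 without duration, −7.00 with a main effect, and −4.91 with duration-by-time. The adjusted group difference after the session went from −7.13 to −5.75.

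**4. Would AIC keep duration?**

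In the change-score model at +10 min, duration was kept in 20% of runs at slope 0, 98% at 0.1 and 100% at 0.2. With the noise doubled, the figures were 32%, 70% and 98%. These depend on the inputs and are not properties of the trial.

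**5. Effect on the test**

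A simpler simulation used one record per participant, 50 per arm and 4000 runs. With no total effect, an arm difference in duration of 0.5 SD and a slope of 0.3, the adjusted analysis rejected in about 11% of runs, against 5% unadjusted. With no direct slope but a shared cause of duration and pain, it rejected in about 9%. With a total effect of 0.5 SD and slope 0.3, the adjusted estimate was about 0.50, 0.42, 0.35 and 0.26 SD for arm differences of 0, 0.25, 0.5 and 0.8 SD.

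**The case against.** The strongest reply is that each text taken alone may be harmless. The body text, with its time points and adjusted values, reads most naturally as a raw-score model, where a duration main effect leaves the change contrast untouched. Appendix A's change-score model has no duration term. Bias in the contrast arises only if the two are combined or a duration-by-time term is added. This is correct, but it does not settle the matter. On the raw-score reading, the adjusted group values that the plan says it reports still move. Appendix A could instead be read as the core model and the body text as adding covariates; that gives exactly the change-score model with duration, where the estimate does move.

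Several other points stand:

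- The text says duration was considered, not retained. Selection is backward, so AIC decides retention, not entry.
- Both arms had the same 30-minute instruction, and no arm difference is documented.
- The two-thirds rule assumes equal slopes for during and after pain and none for pre-session pain. At 10 min and 0.2 mm/min, halving the during slope gives about 1.1 mm and a zero during slope about 0.6 mm. If pre-session pain is related to duration, the shift ranged from about 0.2 to 3.2 mm.
- Duration of exposure could mean time per application; the simulations take it as minutes per session.
- The largest change-score shift shown, 3 mm, is under a third of the MCID.

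**Conclusion.** The concern holds and should be fixed. As written, the rule allows a consequence of assignment to be retained in the model that gives the reported daily-pain results, and nothing settles whether that model or Appendix A's is primary. Confidence that this matters numerically is medium. The shift is zero if session lengths match between arms or are unrelated to pain. For the change contrast it is also zero if duration enters only as a main effect in a raw-score model. Otherwise, under the assumed 5 to 10 minute differences and slopes of 0.1 to 0.3 mm per minute, the change-score estimate moves by 0.5 to 3 mm. The effect of assignment is understated if VR sessions are longer and overstated if they are shorter, given that longer sessions lower pain. These shifts are small against 10 mm but can be a large share of a modest effect: 2 mm of 7 mm in the +10 minute, 0.2 mm per minute example.

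**What to change.** - Remove duration from the candidate terms of the primary daily-pain model.
- State in the Statistical Methods section, in the same words as Appendix A, that the change-score model is the primary analysis: group, time, group-by-time and a participant random effect. Name and fix any baseline covariates, or use none, instead of choosing them by AIC.
- Report minutes per session by arm.
- Label any duration-adjusted or AIC-selected model exploratory.
- Say that this clarification was made after data collection had ended and the data had been explored. Recruitment ran to December 2022, the document is dated May 2023, and the Statistical Methods section already describes findings from data exploration.

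The cost is wording in two places and reanalysis of data already recorded. Carrying the change through the overall analysis and the four per-application analyses, each in the full sample and in the higher-pain subgroup, means about (1 + 4) × 2 = 10 daily-pain models. A small downside is that fixed baseline covariates may include a few uninformative terms.

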Frequency and plans for auditing trial conduct

The independent UBC Behavioural Research Ethics Board was able to audit the study at any time to ensure practices were carried out in accordance with the ethical approval certificate. No audit was carried out during the course of the study.

Plans for communicating important protocol amendments to relevant parties (e.g., trial participants, ethical committees)

All changes to eligibility, recruitment methods, procedures, outcomes, analyses were reported to the UBC BREB for review and approval as post-approval activities, and all changes amended on the clinicaltrials.gov site.

Dissemination plans

This study supports a knowledge translation (KT) process designed to develop theory based on pre-existing innovation, and further define the practical determinants, implementation and uptake considerations for VR use in wider practice. The primary KT target audiences will be healthcare professional groups involved in the management of chronic pain, patients experiencing chronic pain, and their relatives, although we will be careful to avoid prematurely claiming our study findings as generalizable. Health Professional academic/clinical conference presentations will also be undertaken, and it is planned at least three peer-reviewed publications in professional journals will be produced. In addition, a publicly accessible project summary will be sent to all participants and a project website with video and text based resources related to the work has been established at <https://blogs.ubc.ca/arvrha/> where the final report will be posted, with links to the publications arising from it.

Discussion

Due to the global COVID-19 pandemic, the study was paused completely between March 2020 to June 2020. The study was paused two more times (November 2020 - July 2021; Dec 2022) due to pandemic conditions. From June 2020, the study restarted with modified protocols to minimize physical contact and ensure safety according to Behavioural Research Ethics Board guidelines. Participants were screened for COVID-19 exposure and symptoms before each contact. Baseline demographic and outcomes data collection was moved from the set-up session to a teleconference interview session to shorten the session. Participants also received online videos for equipment training to review before the study visit. The set-up session was modified to require personal protective equipment and 2-metre distancing between RA and participant, relying on verbal instructions and demonstrations observed at a distance for training. Weekly check-ins also included screening for COVID-19 symptoms and reassessment of consent. At the end of the participant's 4 weeks, equipment was disinfected during collection then stored in a secure room for 4 days before preparation for use by another participant. When we expanded recruitment across Canada in 2022, we modified the set-up protocol to be completely remote. For participants located outside of BC, participants were shipped all study equipment. For VR, participants received a high-end gaming laptop that could run all VR environments at the highest graphical settings instead of a desktop computer. Participants were asked to view a brief tutorial video on how to set up the equipment. Once the participants received the equipment, an RA would conduct the set-up session via teleconference.

Declarations

Acknowledgements

Appendix A – Detailed Statistical Analysis Plan

1. Objective

Determine the extent to which VR-based applications are advantageous for daily home-based chronic cancer pain management, compared to equivalent applications experienced on two-dimensional (2D) computer screens.

2. Outcomes

This section presents the outcomes investigated to answer the study objective. The analyses are described in section 3.

Primary outcomes

Visual analogue scale pain scores from 0 to 100mm measured before, during and after an immersion for 24 days.

Weekly pain scores measured using the McGill Pain Questionnaire separately for each component sensory pain (11 items), affective pain (4 items), Visual Analogue Scale component scored out of 10 and overall, as a sum for all three components measured at baseline and at week 1, 2, 3 and 4.

Secondary outcomes

Health related quality of life scores measured using physical and mental health components of the short form quality of life questionnaire and the sleep quality index measured using the Pittsburgh Sleep Quality Index all measured at baseline and at week 1, 2, 3 and 4.

3. Population and Subgroup Analyses

Populations

Intention-to-treat (ITT)

All randomized participants will be included in the analysis as allocated to either the intervention or control arm.

Sensitivity analysis

A subgroup analysis of participants with pain scores before an immersion session will be conducted. Analyses for this population will be used to investigate whether conclusions are sensitive to severity of pain before an immersion session.

Subgroup analyses

Four sub-analyses will be conducted for each application. All sub-analyses groups will be conducted for the overall sample and for the sample with severe pain.

4. Data analyses

All outcomes will be presented using descriptive statistics; normally distributed data by the mean and standard deviation (SD) or standard errors (SE) and binary and categorical variables will be presented using counts and percentages. R software version 2.4.3 will be used for all statistical analysis.

The sections below describe analyses that will be conducted in addition to the descriptive statistics.

Primary outcome

The primary analysis will compare mean changes in daily pain before each immersion session and pain scores during and after each session in intervention group to mean changes in daily pain before each immersion session and pain scores during and after each session in control group. Difference in pain score before to time points where it is measured during and after each session (during and after) will be the dependent variable. Study participants will be considered as random effects, treatment group and time together with an interaction term of the treatment group and time as fixed effects. The estimated difference in mean change from before to during, and after immersion sessions and the corresponding 95 % confidence interval (CI) between groups will be presented.

Using a similar approach, the mean changes in weekly pain from baseline measured using the McGill Pain Questionnaire for the overall pain score – combining assessing sensory pain (11 items) and affective pain (4 items) as well as a VAS component scored out of 10, and separately for each component – in intervention group to mean changes in weekly pain in control group will be compared.

Secondary outcomes

Mean changes from baseline in weekly health related quality of life scores and sleep quality index measured using the Health Survey Short Form quality of life and Pittsburgh Sleep Quality Index respectively were compared between the intervention and control groups using the approach like that of weekly primary outcomes.

5. Missing data

When analyzing data for all study participants and those with severe pain, complete case analyses will be conducted for both primary and secondary outcomes. If the number of participants excluded due to missing demographic characteristics is >5% comparisons by assignment arm of those included and those excluded will be conducted to determine if there are any differences in drop out by arm.

References

1. Twombly, R. (2004). What's in a name: who is a cancer survivor? *Journal National Cancer Institute* 96: 1414-15.
2. Canadian Cancer Society and the National Cancer Institute of Canada. *Canadian Cancer Statistics 2008* Toronto: Canadian Cancer Society.

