- **Interventions** - Home-based pain therapy through 4 applications involving cognitive distraction and mindfulness meditation for 30mins/day, 6 sequential days per applications for 4 weeks, either using VR or a 2D laptop.
- **Objective** - Determine to what extent virtual reality (VR) based applications are advantageous for daily home-based chronic cancer pain management compared to equivalent applications experienced on two-dimensional (2D) computer screens.
- **Primary Outcomes** - Daily and weekly pain scores measured via the Visual Analog Scale (VAS) and the Short Form McGill Pain Questionnaire (SF-MPQ).
- **Secondary Outcomes** - Weekly quality of Life (SF-12), and sleep quality (Pittsburgh Sleep Quality Index) were measured.
- **Randomization** - Used a Latin Square design (blocks of 12) to randomize participant arm allocation and sequence of applications experienced.
- **Blinding** - Single blinded (participants were blinded to which NPI they received).

Trial registration: Registered on 16/12/2016 at

<https://clinicaltrials.gov/ct2/show/NCT02995434?term=NCT02995434&draw=2&rank=1> Registration #: NCT02995434

Keywords

Chronic pain, virtual reality, chronic pain, cancer, cognitive distraction and mindfulness meditation.

Introduction

Background and rationale

This study sought to explore the efficacy of virtual reality (VR) as a practical therapeutic intervention in the self-management of the chronic pain associated with cancer survival. This work will inform further clinical studies and future research into the potential uses of VR in the treatment of cancer associated pain. Furthermore, it will help identify optimal VR environments for use in chronic pain applications, practical determinants for implementation of VR for wider practice, and will provide a better theoretical understanding of the mechanisms whereby VR works in chronic pain. Work in this area is in its infancy; VR represents a new technology that has many novel applications. Its value for pain control appears very promising and original clinical work is now essential to establish efficacy and optimal approaches. This proposal builds on results from our current pilot work, and review feedback.

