VR is hypothesized to reduce pain via both active attentional and distractive mechanisms.¹² Neuromatrix theory suggests that pain is a multidimensional experience produced by a *neurosignature*, patterns of impulses generated by a widely distributed neural network, described as the "body-self neuromatrix" in the brain.¹³ VR may work by changing the acuity of the pain modulation system by acting on the signaling pathways of this neuromatrix, producing an analgesic effect. Other researchers suggest that specific cognitive contextual mechanisms in the brain may also help mediate pain.¹⁴

Engaging in a virtual reality experience may therefore, change activity in the bodies' intricate pain modulation system, which in turn have an impact on pain perception. Here the anterior angulate cortex (ACC) region of the brain is suggested to be of particular significance in mediating pain and the ACC is suggested to mediate both attentional processes and emotional reactions in the personal perception of pain.¹⁵ Given these theories, along with rapidly emerging technologies and clinical work in this field, it would appear that VR may have significant potential. However currently there has been little work done to establish the potential use of VR in the management of chronic pain to date, most work on VR for pain management has focused on acute pain via distraction. Several researchers have recommended the investigation of VR for chronic, long term pain^{16,17} and the researchers are currently completing a pilot study to establish best methods and approaches to using VR in chronic pain conditions.

Objectives

This RCT aimed to determine to what extent VR-based applications are advantageous for daily home-based chronic cancer pain management, compared to equivalent applications experienced on two-dimensional (2D) computer screens. To this end, the following null hypotheses were tested:

1. There is no difference between the reported daily pain experiences of participants during, or after exposure to VR immersive environments, overall and within four different VR immersive environments, compared to the equivalent applications experienced on a 2D computer screen.
2. There is no difference in self-reported weekly pain, quality of life, and sleep experiences, of participants exposed to different VR immersive environments over the period of the study, compared to participants exposed to the equivalent applications experienced on a 2D computer screen.

Trial design

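### The by-application sub-analyses estimate VR versus 2D within each environment, but nothing planned tests whether the VR effect on pain differs between environments

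*Combined protocol and SAP*

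**What the plan says.** Appendix A, section 3 (Subgroup analyses): "Four sub-analyses will be conducted for each application". The same paragraph adds: "All sub-analyses groups will be conducted for the overall sample and for the sample with severe pain".

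Appendix A, section 4 (Primary outcome) gives the SAP's model for daily pain. Participants are random effects, with "treatment group and time together with an interaction term of the treatment group and time as fixed effects". The output is "The estimated difference in mean change from before to during, and after immersion sessions and the corresponding 95 % confidence interval (CI) between groups".

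The protocol body (Statistical methods for primary and secondary outcomes) agrees: "Interaction terms of participant exposure and time were included in each model". It also considers baseline demographics and the duration of exposure to each environment for adjustment, and drops terms by AIC. Exposure duration is a covariate for time spent; it does not identify the application.

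Two places say what the by-application results are for. Null hypothesis 1 (Objectives) concerns VR against 2D "overall and within four different VR immersive environments". The Background and rationale says of the work that "it will help identify optimal VR environments for use in chronic pain applications".

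The only comparison between applications that is mentioned is a two-sample t-test on immersion-survey items (video and audio fidelity, cybersickness). None is described for pain, and no multiplicity rule is given for the sub-analyses.

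**The concern.** Each sub-analysis compares the VR-minus-2D difference in one application with zero. Whether that difference varies across applications is another question, and it needs an arm-by-application interaction or a direct contrast. Without one, the only pain results available for comparing environments are four estimates, each with its own interval. A reader may then take an interval that excludes zero for one application, and one that does not for another, as evidence that the first environment works better.

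Separate analyses also leave a strength of the design unused. Each participant is scheduled to use all four applications, one per week, so differences between applications can be assessed within participants.

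At stake are the by-application conclusions and any statement about which environments suit VR.

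**Working it through.** **Inputs from the protocol (Sample size; Participant timeline).** 50 per arm, a 0.5 SD difference, two-sided alpha 0.05, 80% power, RM ANOVA, four applications per participant.

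**Assumed.** The correlation rho between a participant's mean pain changes in two applications is not given, so a range is shown. The 0.5 SD is taken on the scale of those application-level means, with equal variances.

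**The plan's own figure.** For the between-arm effect in an RM ANOVA, lambda = f²·N·m / (1 + (m−1)·rho), with f = 0.25 for 0.5 SD. The number of measurements m and the correlation are not stated.
- With m = 4 and rho = 0.7, lambda = 0.0625 × 100 × 4 / 3.1 = 8.06 and power is 80.3%, so N = 100 is reproduced.
- With m = 2 and rho = 0.5, the required N is 98.

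**One application alone.** This is the case m = 1. The noncentrality of the t-test is 0.5 × √(50/2) = 2.5, which on 98 df gives power of about 70%. Each sub-analysis is therefore weaker than the overall comparison.

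**Four tests against one interaction test.** Simulation with 10,000 trials per setting: four correlated application means per participant, a two-sided 5% t-test per application, and a 3-df arm-by-application F test.

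| rho | Same 0.5 SD effect in all four: tests mixed | Same setting: interaction test rejects | No effect anywhere: at least one of four significant |
|---|---|---|---|
| 0.3 | 63% | 5.5% | 18% |
| 0.5 | 53% | 5.2% | 15% |
| 0.7 | 41% | 5.2% | 14% |
| 0.9 | 23% | 5.1% | 10% |

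A repeat with 40,000 trials per setting agreed to within about one percentage point. If the four tests were independent, the no-effect figure would be 1 − 0.95⁴ = 18.5%.

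The last column is for one time point in one sample. Two time points make 8 tests (1 − 0.95⁸ = 33.7%), and adding the severe-pain sample makes 16 (1 − 0.95¹⁶ = 56.0%). These two figures assume independence and are upper reference values, because the tests are positively correlated.

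**Precision.** Relative to the SE of one application's VR effect, the SE of the difference between two applications' effects is √(2(1−rho)) when the pairing is used. That is 1.18, 1.00 and 0.77 at rho = 0.3, 0.5 and 0.7. If the fits are treated as unrelated it is √2 = 1.41.

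**Power of the interaction test.** If VR helps by 0.5 SD in one application and not at all in the other three, power is about 56%, 72% and 92% at rho = 0.3, 0.5 and 0.7.

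**The case against.** The strongest reply is that the plan does what its hypothesis asks. Null hypothesis 1 is about VR against 2D within each environment, and by-application analyses answer that directly. Neither the Objectives nor Appendix A, section 1 asks whether the effect differs between applications; the wish to help identify optimal environments is one sentence of background. This stands, and it limits the point to comparisons between environments.

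A reader might infer that the plan will present chance differences as real ones. The documents do not support that. They nowhere say that applications will be ranked by significance, and Appendix A promises estimates with confidence intervals. The harm depends on how the results are later read.

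The mixed-result percentages also need care. In that scenario VR works equally in all four applications, so the significant results are correct and the others are missed effects. The figures show that significance patterns are a poor guide to differences; they are not false-positive rates. The no-effect column is a matter of multiplicity, which is related but distinct.

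The wording "Four sub-analyses will be conducted for each application" is ambiguous. It does not say how the sub-analyses are fitted, and it could mean four per application. Separate fits, one per application, are the natural reading; four per application would make multiplicity worse.

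An interaction test has limits too. It compares VR-minus-2D gaps, so an application that relieves pain strongly in both arms shows no larger gap. Control participants used The Witness in place of Carpe Lucem, so contrasts involving that pair mix software with VR. Participants could also change application. These limits call for caution in interpretation; they do not make separate tests a basis for comparison.

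**Conclusion.** The concern holds in a limited form. No application term, arm-by-application term or pain contrast between applications appears in either model description. The planned sub-analyses can address VR versus 2D within each environment but cannot show that the VR effect differs between environments.

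At the protocol's own effect size and 50 per arm, equal true effects would give mixed significance in about 41% to 63% of trials for rho between 0.7 and 0.3, and in about 23% at 0.9. A direct test would reject in about 5%. These figures rest on the assumed correlations, equal variances, and 0.5 SD applying to application-level means.

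It would go too far to conclude that the by-application analyses are invalid or that the overall result is in doubt. They address the hypothesis as written, and the overall VR-versus-2D comparison is unaffected.

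**What to change.** In Appendix A, section 3, for daily VAS change, replace the separate by-application fits with one model on all sessions:
- **Fixed effects:** arm, time point (during or after), application, week, arm-by-time, arm-by-application and arm-by-application-by-time. Keep these terms whatever the AIC.
- **Random effects:** participant and participant-by-application.
- **Application:** as allocated, in line with the intention-to-treat analysis.
- **Report:** at each time point, the four VR-minus-2D differences with CIs and the 3-df arm-by-application test, in the overall sample and in the pre-session pain subgroup.
- **Claims:** say that the VR advantage differs between applications only on that test or on a direct contrast.
- **Caveats:** state that the test compares VR-minus-2D gaps, not which VR environment gives most relief, and that contrasts involving Carpe Lucem and The Witness mix software with VR.
- **Status:** label the analysis as added after data collection, since the trial ran to December 2022.

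The cost is SAP wording and one further model on data already collected. The downside is limited power at N = 100 if correlations are low, so the result may often be no evidence that applications differ.
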